4.4.4. Selection of Doses in the Study

Experience with licensed flavivirus vaccines suggests a 5 mcg dose should be safe and immunogenic; the 5 mcg dose was safe and protective in a NHP model [1]. Therefore, for this trial, subjects were enrolled initially in the 5 mcg group. To determine if lower doses of ZPIV are equally or comparably immunogenic to the 5 mcg dose, subjects were then enrolled in the 2.5 mcg group.

4.4.5. Selection and Timing of Dose for Each Subject

All subjects were scheduled to receive the assigned vaccination on Day 1 and Day 29 (± 3).

4.4.6. Blinding

This is a double-blinded study with the exception of the two sentinel subjects in Group 1. Non-sentinel subjects in Group 1, all subjects in Group 2, investigators, study personnel performing any study-related assessments following study vaccine administration, and laboratory personnel performing assays are blinded to study treatment within a group. The two sentinel subjects received open-label 5.0 mcg ZPIV (i.e., sentinels, investigators and study personnel were not blinded to sentinel study treatment). Laboratory testing personnel remain blinded to the identity and timepoint of individual samples.

The unblinded study vaccine administrator(s) is a study clinician credentialed to administer vaccines but is not involved in study-related assessments or have subject contact for data collection following study vaccine administration.

4.4.7. Prior and Concomitant Therapy

Assessment of study eligibility included a review of all permitted and prohibited medications per the subject inclusion and exclusion criteria. Prescription and over-the-counter drugs and vaccines were recorded, as well as herbals, vitamins, and supplements. Pre-study and concomitant use of any medications, therapies, or vaccines were reported. Medications included all current medications and non-study vaccinations taken within 30 days prior to signing the ICF through approximately Day 29 after the last study vaccination. Subjects who do not receive all study vaccinations would have concomitant medications collected through approximately Day 29 after the last study vaccination, or early termination, whichever occurs first. Subjects presenting with a history of AFI or ARI would have all concomitant medications taken since start of illness recorded.

Medications that might interfere with the evaluation of the investigational vaccine should not be used during the study period unless necessary. Medications in this category include the prohibited medications per the subject exclusion criteria. In addition, the site principal investigator or appropriate sub-investigator may identify other medications that should not be used due to a risk to subject safety or assessment of reactogenicity and immunogenicity. Use of medications as prophylaxis prior to study vaccination was prohibited.

4.4.8. Treatment Compliance

All subjects were to receive a prime dose of vaccine on Day 1 followed by a homologous boost on Day 29. All doses of vaccine were administered in the clinic by a vaccine administrator(s) credentialed to administer vaccines.

4.5. Immunogenicity and Safety Variables

In general, multiple observations within a specific visit period were accepted. In the case of multiple observations within a specific window, the assessment value closest to the scheduled visit date will be used in the analyses for the post-baseline records. If observations have the same distance to the scheduled assessment, the latest one will be used. Unless otherwise specified, the last assessment value recorded prior to the prime dose will be used as baseline. All the recorded data will be listed. Samples from days on which a subject was vaccinated were collected prior to vaccination.

All subjects were to have venous blood samples for assessment of humoral immunity collected on Days 1, 15, 29, 43, 57, 209, 388, and 569. Assay results are reported as the ZIKV titers giving 50% reduction in viral infection (MN50) and IgG ELISA titers. DENV neutralization titers were also to be recorded in subjects reporting ARI or AFI. Samples from the immunogenicity visits immediately before and after the illness visit were used to measure DENV titers, which will be used to aid laboratory confirmation of ZIKV/DENV infection.

Solicited adverse events were collected from the time of study vaccine administration through Day 8 after each dose. Subjects received a memory aid to record any solicited AEs on each day. The following injection site reactogenicity events were measured and grading according to the scale in [Table 3](#) and [Table 4](#): pain, tenderness, pruritis, ecchymosis, erythema, and induration. The following systemic solicited events were measured and graded according to the scale in [Table 4](#) and [Table 5](#): feverishness, fatigue, malaise, myalgia, arthralgia, headache, nausea, vomiting, diarrhea, abdominal pain, rash, and fever.

Vital signs of heart rate and blood pressure were measured in subjects at Days 1, 2, 8, 15, 29, 30, 36, 43, and 57. The measurements were assessed for adverse events of bradycardia/tachycardia and systolic and diastolic hypotension/hypertension according to the scale in [Table 6](#).

Venous blood and urine were collected from subjects on Day 8 and Day 15 following each vaccination for safety clinical laboratory tests. The tests include WBC, hemoglobin, hematocrit, and platelets, ALT, AST, total bilirubin, BUN, creatinine, and urine dipstick for protein and glucose. Laboratory values were assessed for adverse events according to the grading scale in [Table 7](#). Unsolicited adverse events were collected from all subjects through Day 57 (28 days after the 2nd vaccination). These events were assessed for severity and relatedness to study product. Serious adverse events (SAE), adverse events of special interest (AESI), and new onset chronic medical conditions (NOCMC) were collected for the duration of each subject's follow-up. Adverse events of special interest (AESI) for this study are neurologic and neuroinflammatory disorders collected through the duration of the subject's follow-up period.

Subjects were observed for development of an AFI/AI and all related adverse events from the time of signing the informed consent form through follow-up. Subjects who reported an ARI/AI were assessed for the following symptoms which are graded on a scale from 1 (least severe) to 3 (most severe): fever, feverishness, lethargy, restlessness, rash not at injection site, nonpurulent conjunctivitis, headache, shortness of breath, retino-orbital pain, myalgia, arthralgia, arthritis, nausea, abdominal pain, vomiting (evaluated for presence only), and bleeding (evaluated for presence only).

5. SAMPLE SIZE CONSIDERATIONS

The sample size for this study was selected to obtain preliminary estimates of vaccine safety and immunogenicity in a time sensitive manner. This study was not designed to test a specific null hypothesis. As this is a phase I study of ZPIV, it is primarily designed to collect initial information about safety and immune responses of two different doses of the vaccine.

The sample size in each dose cohort is small, thus the precision of estimates for AEs is limited. Rare AEs associated with dose are not demonstrable in a clinical study of this size; however, the probabilities of observing one or more AEs within a dose group at the minimum dose sample size of 35 and among the approximately 80 subjects receiving ZPIV are presented in [Table 8](#). The minimum detectable event rates to achieve various levels of power are also displayed in [Table 9](#).

If there are AEs associated with a particular dose of ZPIV, this study will have at least 80% power to observe at least one such event in a dose cohort if the true rate is 4.5%. If there are AEs associated with ZPIV overall, independent of dose, this study will have approximately 80% power to observe at least one such event in all ZIKV vaccine subjects if the true rate is 2.0%.

The study enrollment plan was modified in protocol amendment 5.0 (18 December 2018) to address the loss of evaluable subjects in Group 1 and delay of enrollment due to Hurricane Maria. The original study design planned to enroll 40 ZPIV recipients and 5 placebo recipients in each Group. Due to Hurricane Maria, 11 subjects enrolled in Group 1 had loss of samples at key timepoints. To rebalance the number of evaluable subjects between Groups, Group 1 enrollment was increased by 5 subjects and Group 2 enrollment was decreased by 5 subjects, for a total enrollment of 50 subjects in Group 1 and 40 in Group 2. Treatment assignments for both groups are assigned according to the originally planned 8:1 ratio of ZPIV:placebo.

6. GENERAL STATISTICAL CONSIDERATIONS

6.1. General Principles

All continuous variables will be summarized using the following descriptive statistics: n (non-missing sample size), mean, standard deviation, median, minimum and maximum, unless otherwise specified. The frequency and percentage of observed levels will be reported for all categorical measures; denominators for percentages will be defined for each analysis.

Listings will be provided for all data. Sort order will be specified on each listing shell in Appendix 3.

Summary tables will be structured with a column for each treatment group (2.5 mcg ZPIV, 5 mcg ZPIV, Placebo) and for all subjects for safety summaries.

All tables will be annotated with the total population size relevant to that table/group, including any missing observations.

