
Enrollment of the 2.5 mcg ZPIV group (Group 2) can begin after or at the same time non-sentinel subjects in Group 1 receive the 1st dose of vaccine. As of December 18, 2017, the majority of non-sentinel subjects in Group 1 have already received the 1st dose and have been followed until Day 8 for safety and reactogenicity, and no halting rules have been met or safety concerns identified. As this is a dose de-escalation study, concurrent enrollment of some remaining non-sentinel subjects in Groups 1 is permitted after enrollment of Group 2 subjects has begun; also, no sentinel subjects will be used in Group 2. All subjects in Group 2 will receive study product or placebo in double-blind fashion.

The original study design planned to enroll 40 ZPIV recipients and 5 placebo recipients in each Group. However, due a natural disaster (hurricane Maria), 11 subjects enrolled in Group 1 had loss of samples at key timepoints. To rebalance the number of evaluable subjects between Groups, Group 1 enrollment will be increased by 5 subjects and Group 2 enrollment will be decreased by 5 subjects, for a total enrollment of 50 subjects in Group 1 and 40 in Group 2. Treatment assignments for both groups will be assigned according to the originally planned 8:1 ratio of ZPIV:placebo. Without compromising the blind of the study, we can anticipate approximately 35 evaluable ZPIV recipients and approximately 5 evaluable placebo recipients in each group.

All subjects will receive a homologous boost of ZPIV or placebo 28 days post-prime if no halting rules precluding second vaccination are met ([Section 9](#)). All subjects will be monitored for occurrence of unsolicited AEs until 28 days after the second vaccination.

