## 11.3 Planned Interim Analyses

### 11.3.1 Analysis Plan

This study has 3 planned interim analyses, all of which will be performed on monitored and locked datasets. The first two interim analyses will consider safety, reactogenicity, and immunogenicity data and will take place at the following time points:

- The first interim analysis will take place after the last subject in Group 1 has been followed through 28 days post-second ZPIV administration (Day 57) and the first interim database has been locked.
- The second interim analysis will take place after the last subject in Group 2 has been followed through 28 days post-second ZPIV administration (Day 57) and the second interim database has been locked.

In these first two interim analyses, safety and reactogenicity data will be summarized in aggregate by enrollment group, while humoral immunogenicity data will be presented by study treatment and pre-vaccination flavivirus immune status. Note that safety/reactogenicity data and immunogenicity data may be presented separately, as results become available.

- The third interim analysis will describe the incidence and severity of AFI/ARI after all subjects have completed one-year follow-up after the 2nd vaccination. In this interim analysis, data will be summarized in aggregate by enrollment group and pre-vaccination flavivirus immune status.

No individual data will be released in any interim analyses. However, these analyses will be made available to the study team and may impact the course of this study, be published, or be used in the planning of future studies.

The interim safety analyses may include tables summarizing demographics, study status, and protocol adherence information. Tables and figures will present unsolicited adverse events by MedDRA System Organ Class (SOC) and Preferred Team (PT), severity, and relationship to study product. Solicited adverse events will be summarized by symptom, severity, and study day. Laboratory results will be summarized by parameter, severity, and study day. Listings of early terminations, protocol deviations, and clinical data may be included.

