1. Number and proportion of subjects who develop an acute febrile illness (AFI) or an acute rash illness (ARI) who have evidence of acute ZIKV or DENV infection detected within 14 days of symptom onset. This endpoint will be analyzed for all subjects overall, and by dosage group, product received, and pre-vaccination flavivirus immune status.
2. Number and severity of laboratory confirmed ZIKV and DENV infections during the study, overall, by treatment group, and pre-vaccination immune status, where severity is described by:
 - Duration of symptoms
 - Grade of symptoms (mild, moderate, severe)
 - Use of concomitant medications
 - Need for hospitalization or other medical care

Laboratory confirmation will be made by AFI or ARI with either: 1) evidence of acute ZIKV and DENV infection within 14 days of symptom onset or 2) a 4-fold rise in DENV or ZIKV neutralization titers between samples collected at the last visit prior to and at the first visit following the AFI/ARI, where available.

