4. INVESTIGATIONAL PLAN

4.1. Overall Study Design and Plan

This study is a single-center, double-blinded, placebo-controlled, Phase 1, dose de-escalation study to evaluate the safety, reactogenicity, and immunogenicity of a purified inactivated, alum-adjuvanted ZIKV vaccine (ZPIV) administered in a homologous prime-boost regimen to healthy male and non-pregnant female adult subjects living in a flavivirus-endemic area. Two dose levels will be evaluated. Each subject will receive either placebo or 5 mcg (Group 1), or 2.5 mcg (Group 2) of ZPIV administered by IM injection. The study will consist of a screening period of up to 28 days, a vaccination period in which subjects will receive a prime dose of vaccine on Day 1 followed by a homologous boost on Day 29, and a follow-up period of 24 months post boost vaccination. See [Table 1](#) of Appendix 1.

As this is a phase I study, the study will begin with enrollment of two sentinel subjects in Group 1 who will receive 5 mcg ZPIV open label. One sentinel subject will be vaccinated, followed for one day for safety and reactogenicity, and if no halting rules are met per determination of the PI and co-PI, then the second sentinel subject will receive 5 mcg ZPIV open-label. Both sentinels will be followed for safety through Day 8 and if no predefined halting rules are met and no safety concerns are identified, then enrollment of the Group 1 non-sentinel subjects will proceed in double-blind fashion. The same procedure will be used for administration of the boost vaccination to the Group 1 sentinels: 1 sentinel will receive 5 mcg ZPIV open-label, be followed for 1 day for safety and reactogenicity, and if no halting rules are met, then the second sentinel will receive the boost vaccine. Both sentinels will be followed until Day 8 after second vaccination for safety and reactogenicity and if no halting rules are then boost vaccination of the non-sentinel Group 1 subjects can proceed. Enrollment of the 2.5 mcg ZPIV group (Group 2) can begin after or at the same time non-sentinel subjects in Group 1 receive the 1st dose of vaccine.

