4.4.3. Method of Assigning Subjects to Treatment Groups (Randomization)

Enrollment/randomization was performed through the enrollment module of AdvantageEDC, the electronic data capture system maintained by the SDCC. The list of randomized treatment assignments was prepared by statisticians at the SDCC and included in the enrollment module for this trial. The electronic data capture system assigned each subject a treatment code after the demographic and eligibility data have been entered into the system. A designated individual at each site was provided with a treatment key, which links the treatment code to the actual treatment assignment, to be kept in a secure place.

At the time of consent and upon entry of demographic data and confirmation of eligibility for this trial, the subject is enrolled. In group 1 (5 mcg ZPIV, N=45; placebo, N=5), two sentinel subjects were enrolled first and received ZPIV in an open-label fashion. All other subjects were randomized in a double-blind fashion. Upon completion of enrollment in Group 1, Group 2 subjects (2.5 mcg ZPIV, N=35; placebo, N=5) were randomized. Subjects received the same study product at their first and second investigational vaccinations.

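### Pooling placebo across two enrolment groups can put half of any between-period difference in illness risk into each dose-versus-placebo contrast

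*SAP*

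**What the plan says.** SAP 6.1 sets the layout for all summaries: "Summary tables will be structured with a column for each treatment group (2.5 mcg ZPIV, 5 mcg ZPIV, Placebo", with an all-subjects column added for safety tables. The AFI/ARI and infection shells (Tables 140-188) follow it.

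Allocation was within group. SAP 4.4.3 reads "In group 1 (5 mcg ZPIV, N=45; placebo, N=5), two sentinel subjects were enrolled first" and then "Upon completion of enrollment in Group 1, Group 2 subjects (2.5 mcg ZPIV, N=35; placebo, N=5) were randomized". On timing the documents disagree. SAP 4.1 says "Enrollment of the 2.5 mcg ZPIV group (Group 2) can begin after or at the same time" as Group 1 non-sentinels receive their first dose, and Protocol section 4 says "concurrent enrollment of some remaining non-sentinel subjects in Groups 1 is permitted after enrollment of Group 2 subjects has begun".

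For exploratory endpoint 1, SAP 3.2 states: "This endpoint will be analyzed for all subjects overall, and by dosage group, product received, and pre-vaccination flavivirus immune status". Protocol 3.2.3 agrees. The protocol summary, Protocol 11.4.4 and SAP 9.9 ask only for treatment group and baseline flavivirus status. Table 1 in both documents heads its first column Dosage Group and lists ZPIV and placebo recipients inside each of Groups 1 and 2.

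The third interim analysis was to be by enrolment group, but with products combined: "data will be summarized in aggregate by enrollment group and pre-vaccination flavivirus immune status" (Protocol 11.3.1).

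**The concern.** AFI, ARI, ZIKV and DENV infection depend on how much virus is circulating while a subject is under observation. A placebo subject is a concurrent control only for the vaccinees of the same enrolment group. Merging the two placebo sets gives a control that belongs fully to neither period, and each dose is then read against it. If risk moved between the periods, one dose would look protective and the other harmful with no vaccine effect.

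Subjects and investigators also knew the group, though not the product (Protocol sections 4 and 5.4.1), so symptom reporting could differ by group as well.

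The final tables would not reveal this. Table 15 gives first-dose dates with placebo pooled, and the listing shells carry treatment group, not enrolment group.

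**Working it through.** **The plan's own figures.** The documents give no figure for AFI/ARI or for any placebo comparison. The sample-size figures (SAP section 5, Tables 8 and 9) are chances of seeing at least one event, 1 - (1 - p)^n. For n = 35 and p = 4.5% this is 80.04%; for n = 80 and p = 2.0% it is 80.14%. Both match the stated 80%. They do not bear on pooling.

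**Inputs.** Planned counts (SAP 4.4.3, Table 1):
- Group 1: 45 ZPIV (including two open-label sentinels) and 5 placebo, or 9:1.
- Group 2: 35 ZPIV and 5 placebo, or 7:1.
- Overall: 80:10, which is the stated 8:1.

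Let p1 and p2 be the risks in Groups 1 and 2 with no vaccine or dose effect, and D = p2 - p1. The documents give neither risk, so the values below are assumptions.

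**Formulas.**
- Pooled placebo = (5·p1 + 5·p2)/10 = (p1 + p2)/2
- 5 mcg minus pooled placebo = p1 - (p1 + p2)/2 = -D/2
- 2.5 mcg minus pooled placebo = p2 - (p1 + p2)/2 = +D/2
- 2.5 mcg minus 5 mcg = D
- All ZPIV minus pooled placebo = (45·p1 + 35·p2)/80 - (p1 + p2)/2 = -0.0625·D
- ZPIV minus placebo within either group = 0, for any p1 and p2

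**Results, in percentage points.**

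| p1, p2 | Pooled placebo | 5 mcg - placebo | 2.5 mcg - placebo | 2.5 - 5 mcg | All ZPIV - placebo |
|---|---|---|---|---|---|
| 10%, 10% | 10.0% | 0 | 0 | 0 | 0 |
| 5%, 10% | 7.5% | -2.5 | +2.5 | +5 | -0.3 |
| 5%, 20% | 12.5% | -7.5 | +7.5 | +15 | -0.9 |
| 10%, 30% | 20.0% | -10 | +10 | +20 | -1.25 |

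If risk falls instead of rising, the signs reverse.

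**Effect of splitting placebo.** Both within-group contrasts become free of D. The raw dose contrast does not change; only the difference between the two within-group contrasts removes D from it.

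**Precision.** At 5% and 20% the standard errors are:
- Group 1 contrast: sqrt(0.05·0.95·(1/45 + 1/5)) = 0.103
- Group 2 contrast: sqrt(0.20·0.80·(1/35 + 1/5)) = 0.191
- Difference of the two: sqrt(0.103² + 0.191²) = 0.217

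The exact 95% interval for 0/5 is 0 to 52.2%; for 0/10 it is 0 to 30.8%.

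**The case against.** The strongest reply is that this is a descriptive Phase 1 trial, that SAP 9.9 plans no AFI/ARI test or vaccine-placebo estimate, and that ten placebo subjects are more informative than five. At 5% and 20% the standard error of 5 mcg minus pooled placebo is 10.7 points, larger than the 7.5-point shift. Observation periods may also overlap: enrolment was expected to take up to 15 months and the tables follow each subject to 12 months after the last vaccination. Overlap would shrink D. All of this stands, and it is why pooled placebo should stay and the split should be supplementary. It does not remove the point, because Protocol 11.1 says vaccine-placebo and between-dose comparisons will be made, and Table 12 applies a Fisher test to withdrawals and discontinuations across three arms with placebo pooled.

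A second reply is that dosage group and treatment group are used interchangeably; the Table 72 shell, for example, treats placebo as a dosage group. That is a fair reading of that shell, but Table 1 uses the term differently. The wording needs aligning either way.

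Three stronger readings might be inferred, and the documents do not support them:
- That calendar changes did produce apparent vaccine effects. No attack rate or transmission trend is given.
- That pooling causes the dose confounding. The dose contrast equals D with placebo pooled or split, and the Table 43 p-values compare the two ZPIV doses only.
- That randomisation is lost altogether. All ZPIV against all placebo moves by only 6.25% of D.

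Stratification of AFI/ARI tables by baseline ZIKV and DENV status is already planned (SAP 6.4, Tables 141-146), so nothing is missing there.

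**Conclusion.** The point holds as a conditional one. With planned placebo counts of 5 and 5, pooling shifts each dose-versus-placebo contrast by half of any between-group risk difference, in opposite directions: 2.5 to 10 points for assumed D of 5 to 20 points, and zero if risk was the same in both periods. Separately, the 5 versus 2.5 mcg comparison carries the whole of D because dose was not randomised, and neither SAP 9.3.1 nor 9.9 says so. The breakdown by dosage group and product received in exploratory endpoint 1 is not delivered by any shell if dosage group has its Table 1 meaning. The third interim cannot stand in for it, as Protocol 11.3.1 has it combine products. How far the two groups overlapped in time decides how large D could be, and SAP 4.4.3 disagrees on that with SAP 4.1 and Protocol section 4.

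**What to change.** - Add supplementary all-subjects versions of the AFI/ARI table (Table 140) and the laboratory-confirmed infection table (Table 147) with four columns: Group 1 ZPIV, Group 1 placebo, Group 2 ZPIV, Group 2 placebo. Footnote the two sentinels as not randomised. Keep the pooled-placebo tables.
- Stratify any vaccine-placebo comparison by enrolment group. For Table 12, replace the three-arm Fisher test with an exact ZPIV-versus-placebo test stratified by group, and report the dose comparison separately.
- State in SAP 9.3.1 and 9.9 that 5 versus 2.5 mcg is a non-randomised comparison of groups enrolled largely in sequence.
- Align the endpoint 1 wording across the protocol summary, Protocol 3.2.3 and 11.4.4, and SAP 3.2 and 9.9. Reconcile the enrolment order in SAP 4.4.3 with SAP 4.1 and Protocol section 4.

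The cost is two tables, one changed test and a few sentences; no new data are needed. The four-column split should not be crossed with serostatus, because cells would often fall below the two-subject minimum in SAP 6.4. The downside is sparse placebo columns: with about 5 subjects each, the split shows the concurrent control but cannot estimate an effect precisely.

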### 11.2 Sample Size Considerations

The sample size for this study was selected to obtain preliminary estimates of vaccine safety and immunogenicity in a time sensitive manner. This study is not designed to test a specific null hypothesis. As this is a phase I study of ZPIV, it is primarily designed to collect initial information about safety and immune responses of two different doses of the vaccine. Due a natural disaster (hurricane Maria), 11 subjects had loss of serum samples at key timepoints and will not be included in any immunogenicity analyses, resulting in approximately 35 evaluable active subjects and 5 placebo subjects in each dose group for those analyses. These 11 subjects will be included in the safety analysis population resulting in approximately 45 active subjects in the 5.0 mcg dose group and 35 active subjects in the 2.5 mcg dose group, for a total of approximately 80 subjects receiving at least one study vaccination of ZPIV.

The sample size in each dose cohort is small, thus the precision of estimate for AEs is limited. Rare AEs associated with dose are not demonstrable in a clinical study of this size; however the probabilities of observing one or more AEs within a dose group at the minimum dose sample size of 35 and also among the approximately 80 subjects receiving ZPIV are presented in the table below. The minimum detectable event rates to achieve various levels of power are also displayed.

If there are AEs associated with a particular dose of ZPIV, this study will have at least 80% power to observe at least one such event in a dose cohort if the true rate is 4.5%. If there are AEs associated with ZPIV overall, independent of dose, this study will have approximately 80% power to observe at least one such event in all ZIKV vaccine subjects if the true rate is 2.0%.

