3.2. Endpoints

Primary Endpoints:

1. Frequency and severity of solicited injection site and systemic reactogenicity from time of study vaccine administration through Day 8 after each administration of study vaccine overall and by dosage group and pre-vaccination flavivirus immune status.
2. Frequency and severity of unsolicited vaccine-related adverse events (AE), including vaccine-related laboratory AE, from first administration of study vaccine until 28 days after the last vaccination overall and by dosage group and pre-vaccination flavivirus immune status.
3. Frequency, type, and duration of serious adverse events (SAE) and adverse events of special interest (AESI) considered related to study vaccine from the first administration of study vaccine until the end of the study overall, and by dosage group and pre-vaccination flavivirus immune status.
4. Frequency of new onset chronic medical conditions reported at any time from the first administration of study vaccine until the end of the study overall, and by dosage group and pre-vaccination flavivirus immune status.
5. Comparison of the frequency, type and duration of vaccine-related Grade 3 local, systemic, or laboratory AE, and Grade 2 or greater local or systemic reactogenicity through Day 8 after each

study vaccine administration between dosage groups and by pre-vaccination flavivirus immune status.

6. Comparison of study withdrawals and discontinuation of study vaccination due to any reason between dosage groups and by pre-vaccination flavivirus immune status.

Secondary Endpoints:

1. Frequency of seroconversion to ZIKV at each post-vaccination visit measured by ZIKV ELISA and neutralization assay in comparison with baseline samples (collected at Visit 00) overall, and by dosage group and pre-vaccination flavivirus immune status.
2. Per Visit GMT as measured by ZIKV ELISA and neutralization assay after each study vaccine administration and for each post-vaccination visit overall, and by dosage group and pre-vaccination flavivirus immune status.
3. Peak GMT as measured by ZIKV ELISA and neutralization assay after each vaccination and overall, and by dosage group and pre-vaccination flavivirus immune status.
4. Proportion of subjects with at least a 4-fold rise in ZIKV GMT as measured by ZIKV ELISA and neutralization assay at 4 weeks after each vaccination compared with baseline overall, and by dosage group and pre-vaccination flavivirus immune status.

Exploratory Endpoints:

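### The only pooled column in the SAP's safety summaries includes placebo recipients, and no table shows all ZPIV recipients combined

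*SAP*

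**What the plan says.** SAP section 6.1 asks for a "column for each treatment group (2.5 mcg ZPIV, 5 mcg ZPIV, Placebo) and for all subjects for safety summaries". The shells in SAP Appendix 1 follow it:

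- Tables 36-42 (overall adverse event summaries), 44-51 (solicited events) and 135-137 (new-onset chronic conditions and related AESIs) have the two dose columns, Placebo and All Subjects. Tables 138 and 139 (related SAEs) are defined by reference to the formats of Tables 110 and 111. Those numbers look out of date, and I read them as the formats of Tables 135 and 137.
- Tables 52-65 (solicited events by reaction and severity) have the three arms and no pooled column.
- Table 43 compares the two ZPIV doses but does not pool them. Tables 66-134 show one arm per table.

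All Subjects is the Safety population, meaning everyone given at least one study vaccination (SAP 6.3.1). Table 36 shows Placebo as one of its columns, so saline recipients are counted in it.

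Primary objective 1 (SAP 3.1) is the safety and reactogenicity of the ZPIV regimen. Primary endpoints 1 and 2 are to be reported "overall and by dosage group and pre-vaccination flavivirus immune status", and endpoints 3 and 4 use nearly the same words. The sample-size section (SAP 5) gives one statement for a single dose cohort, "at least 80% power to observe at least one such event in a dose cohort if the true rate is 4.5" per cent. It gives another for ZPIV at either dose, "approximately 80% power to observe at least one such event in all ZIKV vaccine subjects if the true rate is 2.0" per cent. Protocol section 11.2 gives the same base: "for a total of approximately 80 subjects receiving at least one study vaccination of ZPIV".

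**The concern.** A Phase 1 safety trial of one vaccine at two doses is usually summed up by a statement about everyone who received the vaccine. The sample-size section anticipates such a statement, but the planned tables do not supply it. Someone who wants one overall figure will find only All Subjects, in which about one person in nine received saline.

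The mismatch is plainest for the related SAEs and AESIs, where saline recipients sit in the denominator of a rate of events attributed to the vaccine. At stake is a somewhat low overall rate and a somewhat low upper confidence limit if the pooled column is read as describing ZPIV. The zero-event limit deserves particular attention, because for rare serious events it may be the main thing the trial can report.

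**Working it through.** **Denominators.** From SAP 4.4.3: "In group 1 (5 mcg ZPIV, N=45; placebo, N=5" and "Group 2 subjects (2.5 mcg ZPIV, N=35; placebo, N=5) were randomized".

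- All ZPIV: 45 + 35 = 80
- Placebo: 5 + 5 = 10
- All Subjects: 80 + 10 = 90, so the placebo share is 10/90 = 11.1%

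**The plan's own figures.** The probability of at least one event is 1 − (1 − p)^n.

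- n = 80, p = 2.0%: 1 − 0.98^80 = 80.1%, as in SAP Table 8.
- n = 35, p = 4.5%: 1 − 0.955^35 = 80.0%, as stated.
- The detectable rate at 80% power is 1 − 0.20^(1/n): 1.99% for n = 80 and 4.49% for n = 35, against 2.0% and 4.5% in SAP Table 9.

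The other entries of Tables 8 and 9 also reproduce. With n = 90 the same formulas give 83.8% and 1.77%, so the stated figures describe the 80 ZPIV recipients and not the All Subjects column.

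**Dilution of the rate.** With true rates pV on ZPIV and pP on placebo, the pooled rate is (80·pV + 10·pP)/90. Relative to pV, the shortfall is (1/9)·(1 − pP/pV). It is positive whenever pV exceeds pP. Its maximum is 1/9 = 11.1%, reached when pP = 0. The documents give no expected rates, so these are illustrations:

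- pV = 50%, pP = 10%: (40 + 1)/90 = 45.6%
- pV = 50%, pP = 20%: (40 + 2)/90 = 46.7%

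**Exact (Clopper-Pearson) 95% intervals**, assuming no placebo recipient has the event:

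| Events on ZPIV | All ZPIV, N = 80 | All Subjects, N = 90 |
|---|---|---|
| 0 | 0% (upper limit 4.5%) | 0% (upper limit 4.0%) |
| 8 | 10.0% (4.4 to 18.8) | 8.9% (3.9 to 16.8) |
| 40 | 50.0% (38.6 to 61.4) | 44.4% (34.0 to 55.3) |

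The zero-event limit is 1 − 0.025^(1/N).

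**Can the missing figure be recovered?** The two dose columns are disjoint, and each shows its N and event count. Adding them gives x and N for all ZPIV, and a Clopper-Pearson interval needs nothing else. Medians in the duration tables (137 and 139) cannot be combined from two column summaries. The event listings in Tables 189 and 191 do show treatment group and duration for each event, so those medians can be recalculated too.

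**The case against.** The strongest reply is that All Subjects is a fair reading of the word overall. Protocol section 11.4.2 asks for SAEs and AESIs by study group and also with the groups combined, without leaving placebo out. The first exploratory endpoint in SAP 3.2 attaches overall to all subjects. The column is correctly labelled and sits beside each dose and placebo. The study tests no hypothesis on the pooled rate, and the distortion is small.

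All of that stands, and it rules out several stronger readings that a reader might infer:

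- *That the trial was sized on a rate in 80 recipients which is then lost.* SAP 5 says the size was chosen to give preliminary estimates, with no null hypothesis. The n = 80 statement stands beside one for n = 35. It concerns seeing at least one event, which can be read from the two dose columns.
- *That the exact interval for all ZPIV cannot be obtained.* It can, from counts that are already planned.
- *That All Subjects is offered as the headline vaccine rate.* No passage designates it so.
- *That the SAP departs from the protocol.* Neither document defines overall as vaccine recipients only.

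What the reply does not answer is that, even if overall means all subjects, the group named in the sample-size section has no column, and a pool containing saline recipients does not describe the safety of ZPIV.

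**Conclusion.** The point holds as a reporting gap. The safety summaries pool only into a group of about 90 that includes about 10 placebo recipients, and the roughly 80 ZPIV recipients are nowhere shown together. For the whole Safety population the pooled rate falls short of the ZPIV rate by at most 11% in relative terms when ZPIV exceeds placebo, and the zero-event upper limit is 4.0% instead of 4.5%.

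These sizes assume the planned split of 80 to 10. The bound equals the placebo share, so it may be larger or smaller within an immune-status stratum, and the documents give no stratum sizes. If placebo had the higher rate, the pooled figure would overstate the vaccine rate.

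No test, decision rule or sample-size figure is affected, and the dose-specific results are reported as planned. This is worth correcting because it costs almost nothing. It does not call the validity of the analysis into question.

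**What to change.** - In SAP 6.1, add a column All ZPIV (2.5 + 5 mcg) to Tables 36-42, 44-65 and 135-139.
- Use the statistics each table already has: n, % and exact 95% CI where the table gives intervals; n and % where it does not (for example Table 44); the existing duration summaries in Tables 137 and 139.
- Keep All Subjects where it appears, with a footnote that it includes placebo recipients.
- State that any overall statement about the vaccine is taken from the All ZPIV column.

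The cost is one derived column in 34 shells (7 + 22 + 5). It needs no new data, no new test and no change to the sample-size section.
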